9.5.4 Analyses of Exploratory Efficacy Endpoints in Open-label Treatment Period

For the OLTP of the study, descriptive summaries of efficacy endpoints will be tabulated by visit based on observed data without imputation.

9.6 Safety Analyses

9.6.1 Analyses of Primary Safety Endpoint(s)

For safety endpoints **during the DBTP**, all randomized subjects who received at least one dose of investigational product (ie, Safety Analysis Set) will be analyzed based on

the randomized treatment unless a subject has received the incorrect dose during the entire period of interest (treatment period or study). Safety analyses will be repeated for the non-opioid treated cohort, opioid-treated cohort, and overall. For safety analyses of **vital signs** in OLTP, descriptive summaries of **change from baseline values** will be tabulated based on observed data using pre-OLTP baseline.

No statistical testing comparing treatment groups will be performed in the safety analyses.

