3.2.2 Amgen Investigational Product Background: Erenumab

Erenumab is a human immunoglobulin G2 (IgG2) that is directed against the CGRP receptor complex and inhibits the action of CGRP.

Calcitonin gene-related peptide belongs to the calcitonin family of peptides and is expressed in both the central and peripheral nervous systems. It is prominently involved in the pathophysiology of migraine through nociceptive modulation, in the trigeminovascular system (Goadsby et al, 2002; Tajti et al, 1999). Nonclinical studies with erenumab demonstrated that it binds to and antagonizes both human and cynomolgus monkey CGRP receptors with high affinity and potency. Erenumab has been developed for the prevention of migraine in adults based on the observed long serum half-life in humans (28 days), clinical data demonstrating that small molecule CGRP receptor antagonists are effective in acute migraine reversal (Ho et al, 2008a; Ho et al, 2008b), prevention (Ho et al, 2014), and the strong rationale for CGRP's association with migraine pathophysiology (Goadsby et al 2017; Sun et al, 2016; Bellamy et al, 2006; Sarchielli et al, 2006; Juhasz et al, 2005; Petersen et al, 2005; Lassen et al, 2002; Tajti et al, 1999; Gallai et al, 1995; Goadsby et al 1990; Goadsby et al, 1988).

As of the date of approval of this protocol, erenumab 70 mg and 140 mg SC QM have been approved in the United States, European Union (EU), and other regions for the prevention of migraine in adults.

A detailed description of the chemistry, pharmacology, efficacy, and safety of erenumab is provided in the Investigator's Brochure and regional label.

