
 To explore change in AHMD, MMD, and MHD of at least moderate pain intensity 	
 Change from baseline in mean AHMD, MMD and MHD of at least moderate pain intensity at assessment time points Change from week 24 (OLTP baseline) in mean AHMD, MMD, and MHD of at least moderate pain intensity at assessment time points during OLTP

 To explore everyday activities as measured by the MPFID 	
 Change from baseline in monthly average impact on everyday activities score as measured by the MPFID at assessment time points Change from week 24 (OLTP baseline) in monthly average impact on everyday activities score as measured by the MPFID at assessment time points during OLTP

 To explore physical impairment as measured by the MPFID 	
 Change from baseline in monthly average physical impairment score as measured by the MPFID at assessment time points Change from week 24 (OLTP baseline) in monthly average physical impairment score as measured by the MPFID at assessment time points during OLTP

 To explore the daily activity impact of headache as measured by the HIT-6 	
 Change from baseline in HIT-6 total score at week 52 Change from week 24 (OLTP baseline) in HIT-6 total score at week 52

 To explore migraine-related disability metrics as measured by MFIQ 	
 Change from baseline in MFIQ domain scores and overall impact on usual activities global item score at week 52 Change from week 24 (OLTP baseline) in MFIQ domain scores and overall impact on usual activities global item score at week 52

 To explore migraine-related disability and productivity as measured by the MIDAS Questionnaire 	
 Change from baseline in MIDAS total score, absenteeism score and presenteeism score at week 52 Change from week 24 (OLTP baseline) in MIDAS total score, absenteeism score, and presenteeism score at week 52
Exploratory (Opioid-treated Cohort Only)^a	

Objectives	Endpoints

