3.1 Study Design

Study 20170703 is a phase 4, randomized, double-blind, double-dummy, parallel-group, placebo-controlled study to evaluate the safety and efficacy of erenumab against placebo in a CM population with MOH and prior history of treatment failure. Subjects will be enrolled based on fulfillment of the International Classification of Headache Disorders, 3rd Edition (ICHD-3) CM and MOH criteria and will not be advised to early discontinue acute medication. During randomization, subjects will be separated into 2 distinct cohorts based on their opioid medication use at baseline. Subjects with an opioid medication use > 4 days per month during the baseline period will be allocated to the opioid-treated cohort. Subjects with an opioid medication use of ≤ 4 days per month during the baseline period will be allocated to the nonopioid-treated cohort. The randomization process on the nonopioid-treated cohort will be balanced based on the following stratum:

- Concomitant oral migraine preventive treatment initiated before screening and taken during baseline (Yes or No).

Subjects allocated to the opioid treated cohort will be analyzed separately as an exploratory cohort.

During the DBTP, subjects will be randomized in a 1:1:1 fashion to either placebo, erenumab 70 mg SC every 4 weeks, or erenumab 140 mg SC every 4 weeks. Subjects who successfully complete the 24-week DBTP of the study will be offered an opportunity to continue in an OLTP of 28-weeks duration. Subjects who received erenumab treatment during the DBTP will continue to receive the same erenumab dose during the OLTP. Subjects who received placebo during the DBTP will be allocated in a 1:1 ratio to receive either erenumab 70 mg or 140 mg SC QM during the OLTP. All subjects will remain blinded to their original DBTP treatment assignment.

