5.3 Study Points of Reference

Baseline Assessment

Baseline assessment for the endpoint of the interest is defined as the last non-missing measurement taken or the monthly interval assessed (for endpoints derived from daily eDiary collection) before the first dose of investigational product. In cases where baseline measurements are taken on the same day as IP, it will be assumed that these measurements are taken prior to IP being administered. For subjects who are randomized but not dosed after the randomization, the baseline of the study is defined as the last non-missing measurement prior to or on the date of randomization.

For measurements with multiple individual items, such as MFIQ and ARMR, all individual items from the same set of measurement will be used for analysis.

Pre-OLTP Baseline

Pre-OLTP baseline is defined as the last non-missing measurement for the endpoint of interest taken before the first dose of OLTP IP. In cases where the

measurements are taken on the same day as the first dose of OLTP IP, it will be assumed that these measurements are taken prior to IP being administered. For endpoints derived based on daily eDiary data, the pre-OLTP baseline is the last non-missing monthly measurement before the first dose of OLTP IP.

Study Day 1

Study day 1 is defined as the first IP dose date **regardless on or after randomization date**. For subjects who are randomized but **never received any dose**, the study day 1 is defined as the date of randomization.

Study Day

Study Day is defined as the number of days from study day 1.

Before Study Day 1:

$$\text{Study Day} = (\text{Date of Interest} - \text{Date of Study Day 1})$$

On or after Study Day 1:

$$\text{Study Day} = (\text{Date of Interest} - \text{Date of Study Day 1}) + 1$$

Therefore, the day prior to Study Day 1 is -1.

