9.6.3 Vital Signs

The analyses of vital signs (systolic/diastolic blood pressure (SBP/DBP), **and heart rate**) will include summary statistics of change from baseline over time by treatment group.

Subject incidence at each time-point within the following defined categories for each treatment period:

- Increase from baseline ≥ 10 mmHg in DBP with DBP > 90 mmHg
- Increase from baseline ≥ 10 mmHg in DBP with DBP ≤ 90 mmHg
- Increase from baseline ≥ 20 mmHg in SBP with SBP > 140 mmHg
- Increase from baseline ≥ 20 mmHg in SBP with SBP ≤ 140 mmHg
- Change from baseline in heart rate of ≥ 15 bpm (increase) or heart rate ≥ 120 bpm
- Change from baseline in heart rate of ≤ -15 bpm (decrease) or heart rate ≤ 50 bpm

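### Open-label vital-sign changes are referenced to the pre-OLTP value, which is on-drug for continuing erenumab subjects, so the day-1-to-week-52 change is not explicitly reported and the baseline for the threshold categories is unclear

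*SAP*

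**What the plan says.** - **OLTP change summaries.** SAP 9.6.1 states that descriptive summaries of vital-sign change in the OLTP "will be tabulated based on observed data using pre-OLTP baseline".
- **The two baselines.** SAP 5.3 has separate entries. "Pre-OLTP baseline is defined as the last non-missing measurement for the endpoint of interest taken before the first dose of OLTP IP"; a measurement on the same day counts as pre-dose, so this is normally the week 24 value. The unqualified baseline assessment is the last measurement "before the first dose of investigational product", that is, day 1.
- **Treatment.** SAP 3.1: "Subjects who received erenumab treatment during the DBTP will continue to receive the same erenumab dose during the OLTP". Former placebo subjects are allocated 1:1 to 70 mg or 140 mg.
- **Threshold categories.** SAP 9.6.3 tabulates blood-pressure and heart-rate categories for each treatment period, for example "Increase from baseline ≥ 10 mmHg in DBP with DBP > 90 mmHg". It refers to baseline without saying which one applies in the OLTP.
- **Efficacy, by contrast.** SAP 2.1 lists OLTP efficacy changes from the study baseline and also from week 24, for example "Change from week 24 (OLTP baseline) in HIT-6 total score at week 52".
- **Protocol.** Section 10.4.2.3.4 asks only for vital-sign summary statistics over time by group and does not mention a pre-OLTP reference.

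**The concern.** Vital signs are one of two named safety endpoints, and hypertension is an adverse event of interest in SAP 9.6.2. Subjects in the two erenumab arms have been dosed from day 1 to week 20 when the pre-OLTP value is taken, and the protocol gives a half-life of 28 days, so their reference is an on-drug value. The same label covers an off-drug value for former placebo subjects.

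A change measured from an on-drug reference cannot show whether a rise acquired in the first 24 weeks persisted, and shows only part of a rise that began earlier and continued. What is at stake is the within-subject change over about one year of continuous erenumab. In addition, two programmers could reasonably produce different OLTP category tables from the present text.

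**Working it through.** The plan states no blood-pressure shift, SD or expected incidence, so there is no figure to reproduce. All blood-pressure values below are assumptions.

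**1. Mean change.** Let d be a mean rise complete by week 24 and sustained to week 52.
- From day 1: expected week 52 change = d.
- From pre-OLTP: expected week 52 change = d − d = 0, for any d.

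**2. Which baseline governs the categories.** SAP 9.6.1 assigns the pre-OLTP baseline to OLTP vital-sign change summaries. SAP 9.6.3 says only baseline, which SAP 5.3 defines as the value before first IP. Both readings are open. Steps 3 to 5 show what follows if the categories use pre-OLTP.

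**3. Diastolic rise of at least 10 mmHg at week 52.** The two diastolic categories (above 90, and at or below 90) together cover every such rise. With independent visit errors of SD s, the change has SD s√2, and P(change ≥ 10) = 1 − Φ((10 − d)/(s√2)). From pre-OLTP, d is replaced by 0.

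| Reference and sustained rise | s = 6 | s = 7 | s = 8 |
|---|---|---|---|
| Day 1, d = 5 | 27.8% | 30.7% | 32.9% |
| Day 1, d = 3 | 20.5% | 24.0% | 26.8% |
| Pre-OLTP, any d | 11.9% | 15.6% | 18.8% |

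Example for s = 6, d = 5: s√2 = 8.49, (10 − 5)/8.49 = 0.589, 1 − Φ(0.589) = 0.278. With no drift the two references agree.

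**4. Systolic rise of at least 20 mmHg with SBP above 140, week 52.** Simulated with assumed mean 122, between-subject SD 12 and within-subject SD 8.

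| Sustained shift (mmHg) | Mean change, day 1 | Mean change, pre-OLTP | Flagged, day 1 | Flagged, pre-OLTP |
|---|---|---|---|---|
| 0 | 0 | 0 | 1.3% | 1.3% |
| 3 | 3 | 0 | 2.5% | 1.6% |
| 5 | 5 | 0 | 3.8% | 1.9% |
| 10 | 10 | 0 | 9.5% | 2.4% |

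**5. Single-subject cases (SBP at day 1, week 24, week 40, week 52).**
- 120, 145, 145, 146: changes of 0 and +1 from pre-OLTP, not flagged; +25 and +26 from day 1, flagged at both visits.
- 120, 130, 135, 141: week 52 change of +11 from pre-OLTP, not flagged; +21 from day 1, flagged.
- 125, 125, 146, 146: +21 at both OLTP visits from either reference. A rise that begins after week 24 is captured equally.

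**The case against.** A reader might infer that blood-pressure rises from the double-blind period vanish from the OLTP safety tables and that the one-year safety conclusion is biased. The documents do not support that.

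- **DBTP tables.** SAP 5.4.1 places vital signs up to the first open-label dose in the DBTP, and Table 5-7 windows them at weeks 4 to 24. A rise complete by week 24 is tabulated there against day 1, beside a concurrent placebo arm. In the d = 5 case the week 24 row would show the same 28% to 33%.
- **Categories.** If the default definition in SAP 5.3 governs SAP 9.6.3, the OLTP categories already use day 1 and the percentages above do not apply.
- **Other routes.** Hypertension events of interest are tabulated for the OLTP, and by-visit descriptive statistics (SAP 9.1, protocol 10.4.2.3.4) do not depend on the pre-OLTP baseline.
- **Bias.** The plan states no one-year blood-pressure estimand, does no safety testing and has no control arm in the OLTP. Change during the OLTP is a legitimate period-specific question, and an uncontrolled day-1-to-week-52 change mixes drug effect with time and regression to the mean.

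All four points stand as limits on the claim. They do not fill the gap. The DBTP tables stop at the first open-label dose, so they cannot show persistence or accumulation to week 52. By-visit means show group levels, not which subjects crossed a threshold. Under protocol Appendix 4 a vital-sign abnormality becomes an adverse event only if the investigator judges it clinically significant, so event tables do not replace measured values.

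**Conclusion.** The concern holds in limited form. SAP 9.6.1 ties OLTP vital-sign change summaries to a reference that is on-drug for continuing erenumab subjects and off-drug for former placebo subjects. A sustained DBTP rise contributes about zero to those summaries, and the cumulative change on continuous erenumab is not explicitly reported. That part follows from the definitions and needs no assumed values.

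The effect on the threshold categories is conditional. The contrasts in the working (28% to 33% against 12% to 19% for diastolic, 9.5% against 2.4% for systolic with a 10 mmHg shift) need both the pre-OLTP reading of SAP 9.6.3 and the assumed shifts and SDs. That the text allows either reading is itself worth correcting. Two of the three randomised arms are affected, but OLTP entry is optional after completing the DBTP, so the share of OLTP subjects is not known in advance. This is a cheap improvement to descriptive safety reporting and does not affect the primary analysis.

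**What to change.** In SAP 9.6.1 and 9.6.3:

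1. State the baseline for each OLTP vital-sign table, both the change summaries and the threshold categories.
2. Tabulate OLTP changes and categories from the last value before the first erenumab dose: study day 1 for continuing erenumab subjects, pre-OLTP for former placebo subjects.
3. Show the two groups separately. Their week 52 changes cover about 52 and 28 weeks of exposure, and pooling them would mix the two.
4. Keep the pre-OLTP version as a second table for change during the OLTP.

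The week 40 and week 52 measurements are already scheduled, and there is no effect on alpha. The cost is SAP wording and one extra set of descriptive tables, to be read as uncontrolled.

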9.6.2 Adverse Events

The Medical Dictionary for Regulatory Activities (MedDRA) version 25.1 or later will be used to code all events categorized as adverse events to a system organ class and a preferred term. All AEs will be graded using the Common Terminology Criteria for Adverse Events (CTCAE) Version 4.03. All AE summary tables described below will be summarized by treatment group using subject incidence for the DBTP and be repeated using exposure-adjusted subject incidence for **the DBTP and the OLTP**.

The subject incidence of AEs will be summarized by SOC in alphabetical order and PT in descending order of frequency for all treatment-emergent adverse events (TEAEs), serious AEs, **serious TEAE occurring on or after the COVID infection**, AEs leading to **discontinuation** of investigational product, fatal AEs, **device-related AEs**, and adverse events of interest (EOI) including

- Ischaemic Central Nervous System Vascular Conditions SMQ (Narrow)
- Ischaemic Heart Disease SMQ (Narrow and Broad)
- Peripheral Arterial Disease AMQ (Narrow)
- Hypertension SMQ (Narrow and Broad)
- Constipation AMQ (Narrow and Broad)
- Alopecias AMQ (Broad)
- **COVID-19 SMQ (Narrow)**

Subject incidence of EOI (standardized MedDRA queries [SMQ] and/or Amgen medical queries [AMQ]) will also be summarized according to their categories **by SOC in alphabetical order** and PT in descending order of frequency.

Subject incidence of all TEAEs, SAEs, AEs leading to withdrawal of investigational product, and fatal AEs will be tabulated by PT in descending order of frequency. In addition, summaries of all TEAEs occurring in at least 3% of the subjects by PT in any treatment arm will be provided **by PT** in descending order of frequency.

Summaries of all TEAEs and SAEs will be tabulated by SOC, PT, and grade.

9.6.3 Vital Signs

The analyses of vital signs (systolic/diastolic blood pressure (SBP/DBP), **and heart rate**) will include summary statistics of change from baseline over time by treatment group.

Subject incidence at each time-point within the following defined categories for each treatment period:

- Increase from baseline ≥ 10 mmHg in DBP with DBP > 90 mmHg
- Increase from baseline ≥ 10 mmHg in DBP with DBP ≤ 90 mmHg
- Increase from baseline ≥ 20 mmHg in SBP with SBP > 140 mmHg
- Increase from baseline ≥ 20 mmHg in SBP with SBP ≤ 140 mmHg
- Change from baseline in heart rate of ≥ 15 bpm (increase) or heart rate ≥ 120 bpm
- Change from baseline in heart rate of ≤ -15 bpm (decrease) or heart rate ≤ 50 bpm

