Product complaints	X	X	X	X	X	X	X	X	
Concomitant therapies review	X	X	X	X	X	X	X	X	

Footnotes after last page of table.

Approved

Table 2-2. Schedule of Activities - Study Visits Through Open-label Treatment Period

	Treatment Period								
	Open-label Treatment Period (28 Weeks)								
PROCEDURE	Wk 24 (OLTP Entry Visit)	Wk 28	Wk 32	Wk 36	Wk 40	Wk 44	Wk 48	Wk 52/ EOS ^a	Notes
LABORATORY ASSESSMENTS									
Urine pregnancy test (females of childbearing potential only) ^d	X	X			X			X	
Urine drug test	X (to be performed at the discretion of the investigator)								
Chemistry	X (to be performed at the discretion of the investigator)							X	
CLINICAL OUTCOME ASSESSMENTS/PATIENT-REPORTED OUTCOMES									
Site re-assigns eDiary to subject					X				
eDiary					X (Daily)				Daily during assessment study months
Subject brings eDiary to center for use during visit or to return								X	Sites should retain eDiary at EOS visit
MPFID					X (Daily)				Daily during assessment study months
HIT-6								X	eDiary in clinic
MFIQ								X	eDiary in clinic
MIDAS								X	eDiary in clinic

Footnotes after last page of table.

Approved

Table 2-2. Schedule of Activities - Study Visits Through Open-label Treatment Period

	Treatment Period								
	Open-label Treatment Period (28 Weeks)								
PROCEDURE	Wk 24 (OLTP Entry Visit)	Wk 28	Wk 32	Wk 36	Wk 40	Wk 44	Wk48	Wk 52/ EOS ^a	Notes
STUDY TREATMENT									
Subject receives training on usage of autoinjector	X								
Self-administration of investigational product at clinic	X	X			X				
Self-administration of investigational product at home			X	X		X	X		
Study staff dispenses and/or reconciles investigational product		X			X			X	
Amgen investigational product ^e	X	X	X	X	X	X	X		Autoinjectors

Page 3 of 3

BP = blood pressure; DBTP = double-blind treatment period; eDiary = electronic diary; EOS = end of study; ET = early termination; HIT-6 = Headache Impact Test-6; HR = heart rate; **IRT = Interactive Response Technology**; MFIQ = Migraine Functional Impact Questionnaire; MIDAS = Migraine Disability Assessment; MPFID = Migraine Physical Function Impact Diary; OLTP = open-label treatment period; RR = respiratory rate

^a A subject who discontinues investigational product during the OLTP or who completes the study will perform the week 52/EOS visit assessments. Subjects who early terminate will complete the assessments approximately 28 (+3) days after the last dose of investigational product.

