^b All subjects will be enrolled via **IRT** in the OLTP to maintain the initial treatment blinding in DBTP. Subjects who received active treatment during the DBTP will remain on the same dose. Subjects who received placebo will receive either 70 mg or 140 mg in a 1:1 ratio.

^c Including pre-filled syringe in DBTP and autoinjector during OLTP.

^d Additional on-treatment local laboratory pregnancy testing may be performed at the investigator's discretion if there is suspicion that a female subject is pregnant or per local laws and regulations.

^e Study drug supply ceases at week 48.

Approved

Table 2-3. Schedule of Activities – Optional Interview-based Substudy (Selected US Sites Only)

PROCEDURE			Treatment Period							Notes
	Screening Period	Baseline Period	Double-blind Treatment Period (24 Weeks)							
	(up to 3 weeks before Baseline)	(4 weeks before Day 1)	Day 1 (post-rand)	Wk 4	Wk 8	Wk 12	Wk 16	Wk 20	Wk 24/ ET	
INTERVIEW-BASED SUBSTUDY										
Substudy informed consent			X ^a							
Substudy Eligibility Requirements			X							
Interview ^b			X ^c						X ^d	

DBTP = double-blind treatment period; ET = early termination; US = United States.

^a The Substudy subject informed consent can also be obtained at the same time as the main study informed consent during Screening instead of after randomization.

^b The first interview (Interview 1) will be conducted within the first week after randomization, the second interview (Interview 2) will be conducted within 1 week after the subject's last visit during the DBTP.

^c The entry interview will be conducted within 7 days from first investigational product dose.

^d The exit interview will be conducted in close proximity with the week 24 or early termination visits (within 7 days prior to week 24 visit or within approximately 14 days post early termination visit. If possible within 7 days post early termination will be targeted).

Approved

3. Introduction

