9.1.3 Early Termination

Upon permanent discontinuation from the study for any reason other than study completion or withdrawal of consent, an ET visit will be performed approximately 28 days after the last dose of investigational product.

Subjects who early terminate the study before week 24 should complete the week 24/ET assessments ([Table 2-1](#)).

Subjects who early terminate the study after week 24 and before week 52 should complete the week 52/EOS assessments ([Table 2-2](#)).

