5.4.3 Analysis Visits for Endpoints Based on Monthly Collection

Since the actual visit for a subject may not exactly coincide with their targeted visit date, the actual visit date is mapped to the analysis visit as in [Table 5-2](#) to [Table 5-7](#).

By-visit data collected on or before the first OLTP dose date belong to DBTP. Data collected after the first OLTP dose date, not including the safety follow-up visit, belong to OLTP. Any data occurred after EOS date will not be included in the analysis except antibody data.

For by-visit summaries, if more than one visit with non-missing measurement (including the unscheduled visits, ie, CPEVENT = 'UNSCHED') fall within the same visit window, the following rules will be applied according to the order described below for selecting one visit per visit window for summary:

1. Scheduled visit will be used regardless of the distance from the target day. Unscheduled visit will only be used when there is no measurement from scheduled visit in the visit window.
2. The visit closest to the target day will be considered for analysis.
3. If two assessment dates are equidistant from the target date, the latter visit will be considered for analysis.

Table 5-2. HIT-6 and MFIQ Analysis Visit Windows

Study Period	Analysis Visit	Target Day	Visit Window (Study Day)
Double-blind Treatment Period	Day 1 (Baseline)	1	Last measurement prior or on Day 1
	Week 4 (Month 1)	29	16 to 43
	Week 8 (Month 2)	57	44 to 71
	Week 12 (Month 3)	85	72 to 99
	Week 16 (Month 4)	113	100 to 127
	Week 20 (Month 5)	141	128 to 155
	Week 24 (Month 6)	169	156 to Week 24 dose date, if available, else to 183
Open-label Treatment Period	Week 52 (Month 13)	365	352 to 379

Table 5-3. MIDAS Analysis Visit Windows

Study Period	Analysis Visit	Target Day	Visit Window (Study Day)
Double-blind Treatment Period	Day 1 (Baseline)	1	Last measurement ≤ Day 1
	Week 12 (Month 3)	85	72 to 99
	Week 24 (Month 6)	169	156 to Week 24 dose date, if available, else to 183
Open-label Treatment Period	Week 52 (Month 13)	365	352 to 379

Table 5-4. ASC-12/GAD-7/BDI-II/Sleep Questionnaire Analysis Visit Windows

Study Period	Analysis Visit	Target Day	Visit Window (Study Day)
Double-blind Treatment Period	Day 1 (Baseline)	1	Last measurement ≤ Day 1
	Week 12 (Month 3)	85	72 to 99
	Week 24 (Month 6)	169	156 to Week 24 dose date, if available, else to 183

Table 5-5. PGIC Analysis Visit Windows

Study Period	Analysis Visit	Target Day	Visit Window (Study Day)

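### The vital-sign outlier tables have no any-time count, and the open-label windows leave early-termination readings unassigned for five of six last-dose positions

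*SAP*

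**What the plan says.** **Counting rule.** SAP 9.6.3 lists six threshold categories for diastolic pressure, systolic pressure and heart rate. They are to be reported as "Subject incidence at each time-point within the following defined categories for each treatment period". The section also plans change from baseline over time. It names no worst-value or any-time summary.

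**Selection rule.** SAP 5.4.3 says that "the actual visit date is mapped to the analysis visit as in" Tables 5-2 to 5-7, and Table 5-7 is the vital-sign table. Where a window holds several measurements, the rules are for "selecting one visit per visit window for summary". The first rule is "Scheduled visit will be used regardless of the distance from the target day", followed by "Unscheduled visit will only be used when there is no measurement from scheduled visit in the visit window".

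**Windows.** In the DBTP, Table 5-7 runs without a break from day 16 to day 183 (or to the week 24 dose date). In the OLTP it has two windows: week 40 (days 268–295) and week 52 (days 352–379). It has no row for early termination.

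**When OLTP vital signs are taken.** Protocol Table 2-2 schedules them at week 24, week 40 and week 52/EOS. Protocol 9.1.3 adds: "Subjects who early terminate the study after week 24 and before week 52 should complete the week 52/EOS assessments". Table 2-2, footnote a, gives the timing: "Subjects who early terminate will complete the assessments approximately 28 (+3) days after the last dose of investigational product". The last possible dose is at week 48 ("Study drug supply ceases at week 48").

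**The concern.** Vital signs are one of the two safety endpoints named in the objectives, and hypertension is an adverse event of interest in SAP 9.6.2. The thresholds in SAP 9.6.3 give an objective numeric count that does not depend on an investigator deciding to report an event. That count can include only readings that survive the window rules.

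Two kinds of reading do not survive. One is an unscheduled reading that shares its window with a scheduled one, or that falls in no window. The other is the end-of-study reading of a subject who leaves the OLTP early, whenever its date falls between the two OLTP windows. The second loss is the larger defect, because the protocol requires that reading and the plan then gives it no analysis visit. The OLTP tables would then lean towards subjects who stay on treatment. Former placebo subjects first receive erenumab in the OLTP, so those who leave soon after entry could have no scheduled on-erenumab vital sign tabulated at all.

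**Working it through.** **1. Reproduce Table 5-7.** Target day = 7 × week + 1; window = target − 13 to target + 14. Week 40: 7 × 40 + 1 = 281, window 268–295. Week 52: 7 × 52 + 1 = 365, window 352–379. The same formula returns all eight post-baseline rows of the table (week 24 ending at day 183 when there is no week 24 dose date).

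**2. Date the OLTP early-termination visit.** Nominal day = 7 × (week of last dose) + 1 + 28. For the range, the dose visit may move by ±3 days (Protocol 9.1.2) and the termination visit by 0 to +3 days (Table 2-2, footnote a), which gives nominal − 3 to nominal + 6.

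| Last dose | Nominal day | Range | Window |
|---|---|---|---|
| Week 24 | 197 | 194–203 | none |
| Week 28 | 225 | 222–231 | none |
| Week 32 | 253 | 250–259 | none |
| Week 36 | 281 | 278–287 | Week 40 |
| Week 40 | 309 | 306–315 | none |
| Week 44 | 337 | 334–343 | none |

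A last dose at week 48 gives day 365 (362–371), inside the week 52 window, but that is normal completion. So five of the six early positions are unassigned.

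**3. Stretch the timing.** The protocol says approximately 28 days. Allowing 28 ± 7 days as well as the ±3-day dose tolerance gives nominal ± 10. The closest approaches are then day 263 (week 32) against a window opening on day 268, day 299 (week 40) against one closing on day 295, and day 347 (week 44) against one opening on day 352. The count remains five of six.

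**4. Which subjects have nothing else.** After the first open-label dose, the only scheduled vital signs are at week 40 and week 52/EOS. A subject who terminates after a week 24, 28 or 32 dose never reaches week 40, so the termination visit is the only scheduled OLTP reading, and it has no window. After a week 40 or 44 dose, the week 40 reading is tabulated and the termination reading is not.

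**5. From positions to subjects.** The documents give no distribution of termination times. Under assumed weights across the six positions, the unassigned share is:
- equal weights: 5/6 = 83%
- weights falling from 6 to 1: 18/21 = 86%
- weights rising from 1 to 6: 17/21 = 81%
- week 36 three times as likely as each other position: 5/8 = 62.5%
- week 36 five times as likely: 5/10 = 50%

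**6. The DBTP.** The same formula for last doses at day 1 and weeks 4, 8, 12, 16 and 20 gives days 26–35, 54–63, 82–91, 110–119, 138–147 and 166–175. All lie inside Table 5-7 windows. What can be lost is an unscheduled reading that shares a window with a scheduled one, or any reading on days 2–15.

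**The case against.** The strongest reply is that the placebo-controlled comparison is barely touched. DBTP windows are contiguous from day 16, every DBTP early-termination position is captured, and subjects who stop product in the DBTP are asked to complete the remaining visits. The gap lies in an uncontrolled period, summarised descriptively and without testing. All of this stands. A reader might infer that a subject who stops erenumab for raised blood pressure would usually be missing from every vital-sign table. The documents do not support that: it is false for DBTP early terminators, and a high reading at a scheduled visit that falls in a window is tabulated.

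Second, adverse-event reporting offers another route. Clinically significant vital-sign findings count as adverse events (Protocol Appendix 4), and SAP 9.6.2 tabulates events leading to discontinuation and the Hypertension SMQ. This also stands, but only in part: it depends on investigator judgement and does not supply the numeric threshold counts that SAP 9.6.3 sets out to give.

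Third, SAP 5.6 defines subject incidence within a period as at least one occurrence, which might be read as already giving an any-time count. It does not settle the matter, because SAP 9.6.3 ties the categories to each time-point.

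Fourth, three further inferences go too far:
- **Day coverage.** The OLTP windows cover 42 of the 196 days from day 170 to day 365 (21%). This says little, since vital signs after OLTP entry are scheduled only at weeks 40 and 52, and both have a window.
- **Product discontinuation.** The 28-day timing is attached to early termination. Protocol 8.1 sends OLTP product discontinuers to the week 52 procedures without that timing, and a visit actually held at week 52 would be captured.
- **Discarded readings.** The readings are left out of the by-visit tables, not deleted from the data. That they are the ones most likely to be abnormal is plausible, but nothing in the documents shows it.

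**Conclusion.** The point holds in limited form. As written, the plan has no any-time count for the vital-sign categories. For OLTP early terminators, the required end-of-study reading has no analysis visit after a last dose at week 24, 28, 32, 40 or 44. For the first three of those positions, the subject contributes no scheduled reading to the by-visit OLTP vital-sign tables.

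Five of six counts dosing positions, not subjects. It rests on the 28-day timing in Table 2-2 and on mapping by actual date, and it survives a ±7-day stretch of that timing. Neither the number of OLTP early terminators nor their timing is given, so the effect on incidence cannot be sized. The DBTP comparison is affected only through unscheduled readings displaced by a scheduled one and readings on days 2–15. This is an inexpensive gap to close for a named safety endpoint; it does not undermine the controlled safety comparison.

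**What to change.** In SAP 9.6.3, add for each treatment period the subject incidence of each category at any post-baseline reading, counting scheduled, unscheduled and early-termination/EOS measurements. In Table 5-7, add an early-termination/EOS row for OLTP vital signs so that these readings have a defined place. Keep the by-visit tables as they are.

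The cost is SAP wording and one extra table per period; the readings are already collected and the protocol need not change. The downside is that any-time incidence will be higher than by-visit incidence, because it picks up transient readings. In the DBTP this should be comparable across arms. The OLTP has no placebo arm, so its figure should be presented as descriptive only.
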